### 1.2 Secondary objective

- To assess overall survival (OS) of patients with AML treated with lenalidomide maintenance.
- To assess event-free survival (EFS) of patients with AML treated with lenalidomide maintenance.
- To assess the duration of remission (CRd) of patients with AML treated with lenalidomide maintenance.
- To assess toxicity and safety of lenalidomide maintenance in patients with AML.
- To assess the effects of lenalidomide maintenance on NK cell modulation and dynamics of minimal residual disease and their relationship to outcomes.

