## 5.2 During treatment Evaluation.

- a. Physical examination (including vital signs, weight, performance status) every 28 days ( $\pm 7$  days) for the first 3 months, then every 3 months until 12 months from the start of therapy; then every 6 months ( $\pm 2$  months).
- b. CBC with differential (differential not required if  $WBC \leq 0.5 \times 10^9/L$ ), at least once weekly for the 1st cycle, then every 2 to 4 weeks during cycles 2-6, and then every 4 weeks ( $\pm 14$  days) thereafter as long as they are on study.
- c. Serum chemistry profile at least once weekly for the 1st cycle, then every 2 to 4 weeks during cycles 2-6, and then at least every 4 weeks ( $\pm 14$  days) during active treatment.
- d. Bone marrow aspiration and/or biopsy after cycle 1, after 3 months of therapy ( $\pm 2$  weeks), then every 3 months ( $\pm 1$  month) until month 12, then every 6 months ( $\pm 2$  months). No repeat bone marrow is necessary if non-response or progressive disease can be unequivocally diagnosed from peripheral blood tests or, in patients with a  $WBC < 0.4 \times 10^9/L$ , if the bone marrow is considered non-contributory by the investigator at any point.
- e. Flow cytometry for MRD after cycle 1, after 3 months of therapy ( $\pm 2$  weeks), then every 3 months ( $\pm 1$  month) until month 12, then every 6 months ( $\pm 2$  months).
- f. Peripheral blood for correlative immune studies once weekly for the 1st cycle, and once at the end of cycle 3, 6, and 12. (if patient agrees to correlatives)
- g. Patients will be followed for survival every 6 to 12 months after completion of active treatment and while still on study or be enrolled on the leukemia department long-term follow-up umbrella protocol.
- h. Women of child bearing potential must have a negative pregnancy test prior to each cycle of therapy.

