### **7.5 CORRELATIVE STUDIES**

Collection of Immune Modulation Studies will be requested from all patients on study. Heparanized blood specimens will be collected for assays to assess correlates of immune system activity prior to beginning treatment, at day 7, 14, 21, and 28 of Cycle 1 ( $\pm$  3 days), and at the end of Cycle 3, 6 and 12 ( $\pm$  14 days). The assays include:

1. Enumeration of immune cells (by multi-parameter flow cytometry)
2. Quantification of cytokines/chemokines (by Luminex® Multiplex assay)
3. NK cell functional assay (by Calcein-release direct cytotoxicity)
4. KIR genotyping (by SSP- or SSO-PCR analysis)
5. NK cell gene expression profile (using custom NK cell codeset on the nanoString platform)

These assays will be used to identify biological correlates of lenalidomide immune-modulatory activity, and to correlate immune function, genotype, and immunomodulation with disease response or relapse.

Sample requirements:

10 mL of blood drawn into a sodium heparin (green top) tube.

Sample preparation/handling:

Keep samples at room temperature. Notify the [name] Lab by email for same-day sample pickup. Use pager or phone as backup contact:

[name]

e-mail: [[contact]](mailto:[contact])

[contact]

[contact]

[name]  
 e-mail: [[contact]](mailto:[contact])  
 [contact]

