## 8.0 STATISTICAL CONSIDERATIONS

### STATISTICAL CONSIDERATIONS

This is a phase II study of lenalidomide as a maintenance therapy in patients with high risk AML and in first or second remission. The primary objective is to assess whether the maintenance therapy can improve relapse-free survival (RFS), which is defined as the time interval from date of treatment start until the date of death or disease relapse. Patients who are alive and relapse-free at the last follow-up date will be censored at that time.

The study will be continuously monitored for the primary endpoint, RFS, using the method of Thall, Wooten, and Tannir (2005). Our goal is to improve the median RFS from 8 months (based on historical treatment) to 10.5 months using lenalidomide maintenance therapy. It is assumed that the RFS time is exponentially distributed with a median of  $\lambda_E$  among patients who receive lenalidomide as a maintenance therapy, and a median of  $\lambda_H$  is assumed for the historical treatment. Further, we assume that  $\lambda_H$  follows an inverse gamma distribution, i.e.,  $\lambda_H \sim \text{IG}(3.6, 20.8)$ , which has a mean of 8 months and variance of 40. To reflect the little prior knowledge of  $\lambda_E$  we assume an inverse gamma prior distribution with the same mean of 8 months and a much larger variance of 500, i.e.,  $\lambda_E \sim \text{IG}(2.128, 9.024)$ . The trial will be stopped early if  $\text{Pr}(\lambda_E > \lambda_H + \delta | \text{data}) < pL$ , where  $\delta = 2.5$  months and  $pL=0.05$  and this futility monitoring rule will be first applied when 10 patients have been enrolled. A maximum of 50 patients will be enrolled into this study at an expected accrual rate of 1 patient per month. From historical experience, 25% of patients in this cohort may become eligible for stem cell transplant and may come off study. For purposes of this analysis, these patients will be censored at the time of receiving transplant. Patients will be followed up for an additional 12 months after all patients have been enrolled. The trial will be conducted using the Clinical Trial Conduct (CTC) website maintained by the Department of Biostatistics at MDACC.

The operating characteristics of the design, based on an overall assumed accrual rate of 2 patients per month with 5000 simulated trials per scenario, are given in the following table. One-Arm Time-to-Event Simulator (version3.0.1) was used for the design and simulation.

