#### Operating characteristics for Toxicity Monitoring

True Toxicity Rate	Early Stopping Probability	Sample Size		
		25 th percentile	Median	75 th percentile
0.10	0.0002	50	50	50
0.20	0.010	50	50	50
0.30	0.135	50	50	50
0.40	0.542	20	40	50
0.50	0.904	10	20	30

The correlative biology studies are considered exploratory; trends and associations will be used to gain insight into the potential activity of this regimen and to help select potential biomarkers for further investigation in follow-up studies.

Correlative data will be reported by dose level with simple summary statistics: means (possibly after transformation) or medians, ranges, and standard deviations (if numbers and distribution

permit). Scatterplots will be used to explore possible associations between the dose and the immunomodulatory parameters, and between the immunomodulatory parameters and toxicity experienced (as reflected in the maximum grade of toxicity experienced or in clinical measurements). Scatterplots will also be used to explore possible associations between the immunomodulatory parameters, MRD, and relapse.

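### Immune markers and MRD are related to relapse only by scatterplot, with no rule for censoring, transplant or lost later samples; this can create false associations if the plotted summary depends on time on study

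*Combined protocol and SAP*

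**What the plan says.** Section 1.2 lists as a secondary objective the effect of lenalidomide on NK cells and the "dynamics of minimal residual disease and their relationship to outcomes".

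Section 7.5 schedules immune samples before treatment, "at day 7, 14, 21, and 28 of Cycle 1", and "at the end of Cycle 3, 6 and 12". It says the assays will be correlated with response or relapse. Section 5.2 schedules "Flow cytometry for MRD after cycle 1, after 3 months of therapy", then three-monthly to month 12 and six-monthly after that.

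The closing paragraphs of section 8.0, after the toxicity operating characteristics, state that "The correlative biology studies are considered exploratory" and that the results will help choose biomarkers for later studies. The methods are summary statistics by dose level and scatterplots. For outcome the whole instruction is: "Scatterplots will also be used to explore possible associations between the immunomodulatory parameters, MRD, and relapse". The text does not define relapse as a yes/no or a time, name the visit or summary to be plotted, or address patients who are censored, transplanted or never sampled.

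For RFS itself, section 8.0 does have such rules: censoring at last follow-up, censoring at transplant, and a secondary competing-risk analysis for transplant. They are not extended to the correlative work.

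**The concern.** The samples at the end of cycles 3, 6 and 12, and the later MRD assessments, come from a shrinking and selected group. A patient who relapses, dies or is transplanted early contributes mainly early samples, and one who stays in remission contributes late ones. If a marker changes with time on drug, any per-patient summary that depends on how long the patient was sampled (last value, maximum, all visits pooled) is tied to follow-up time, whether or not the marker has anything to do with relapse. Such change is plausible here, because section 2.4 rests on lenalidomide raising NK cell numbers and activity. A scatterplot also has no way to show that some relapse times are censored.

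At stake is the choice of biomarkers for follow-up studies. A marker could be carried forward because it tracks length of observation.

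**Working it through.** The plan gives no sample size, power or error rate for the correlative analysis, so there is no figure of its own to reproduce.

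**Step 1: who is left to be sampled.** Section 8.0 supplies the model: "It is assumed that the RFS time is exponentially distributed", and the goal is to "improve the median RFS from 8 months (based on historical treatment) to 10.5 months". With t in months (28 days = 0.92 months), the relapse-free share is S(t) = exp(−ln 2 × t / median). For example, the end of cycle 12 is day 336 = 11.04 months, so S = exp(−0.693 × 11.04 / 8) = 0.38.

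| End of cycle | Median 8 months | Median 10.5 months |
|---|---|---|
| 1 (day 28) | 92% | 94% |
| 3 (day 84) | 79% | 83% |
| 6 (day 168) | 62% | 69% |
| 12 (day 336) | 38% (19 of 50) | 48% (24 of 50) |

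Section 8.0 expects about 25% of patients to become eligible for transplant. If 25% are transplanted before relapse at a constant hazard h, then h/(h + λ) = 1/4, so h = λ/3, and the share free of both is exp(−(4/3) × ln 2 × t / median). At the end of cycle 12 this is 28% or 38% (14 or 19 of 50).

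**Step 2: what a naive plot does with a null marker.** Simulated trials had 50 patients, exponential RFS, 12 months of follow-up after the last enrolment, the section 7.5 sampling times, and a marker with no effect on relapse. Accrual was 1 per month (section 8.0 text) or 2 per month (its simulations). Drift and variability are assumptions, because the documents give none. One setting used patient SD 1, error SD 0.5 and drift of 0, 0.05 or 0.10 SD per month. The other used within-patient correlation 0.5, transplant as above, and drift of 0, 0.5 or 1 SD by cycle 12 (1/11.04 = 0.09 SD per month at most).

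Share of trials with p < 0.05:

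| Plot | No drift | Middle drift | Largest drift |
|---|---|---|---|
| Last value against RFS time | 5–6% | 21–23% | 62–66% |

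- Mean correlation of last value with RFS time: about 0, 0.17 and 0.32–0.33. With drift of −0.10 SD per month it is −0.32.
- Last value against relapse yes/no: about 3% to 12% over all settings.
- Value at one fixed visit, among patients with that sample: about 5% at every drift.
- Maximum value against RFS time: 14–17% even with no drift (correlation 0.5).

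**Step 3: transplant related to the marker.** The fixed-visit result assumes that transplant is unrelated to the marker. If the transplant hazard rises by an assumed factor of 1.5 to 2 per SD of the marker, a baseline value against relapse yes/no gives 10–37%, and among patients sampled at cycle 3 it gives 7–22%.

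**Step 4: the alternative.** On the same null data, Cox score tests gave 4–7% from a cycle 3 landmark, 4–6% from the baseline value, and 4–6% as cause-specific tests when transplant depended on the marker.

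**The case against.** The plan calls this work exploratory, names no test or p-value, and hangs no trial decision on it. A scatterplot of one fixed visit against later relapse would be close to unbiased if transplant is unrelated to the marker. The large error rates belong to one reading, last value against RFS time. Five of the eight immune time points are at baseline or in cycle 1, where few patients have been lost, and KIR genotype does not change. Immune sampling also depends on patient agreement (sections 5.1 and 5.2), so 50 is a ceiling: in the worst case above, about 65% falls to about 48% with 35 patients and 36% with 25.

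All of this stands, and it limits the point. It does not remove it, because the plan does not confine itself to the safe version and intends to use the results to choose biomarkers.

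A reader might go further in three ways that the documents do not support:

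- That the planned plots will create false associations. They can, depending on a summary the plan leaves open.
- That any drifting marker will look protective. A rising one would; a falling one would look harmful; at a fixed visit drift produces nothing.
- That late samples exist only for relapse-free patients. Section 4.0 lets some patients stay on study after a relapse that is not clinically significant. Samples taken after relapse raise a different problem, since the marker may then reflect the relapse.

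**Conclusion.** The concern holds in conditional form and is minor. For a listed secondary objective, the only planned link between on-treatment markers or MRD and relapse is a plot that does not handle censoring, transplant or the loss of later samples. On the plan's own RFS model, 52% to 62% of patients would have relapsed or died by the cycle 12 sample (100% − 48% and 100% − 38%). Nominal false positives run from about 5% (fixed visit, or no drift) to about 65% (last value against RFS time, drift of 0.10 SD per month).

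The relapse-free shares rest only on the plan's exponential model and medians. The error rates rest on assumed drift, variability and transplant effects, and should be read as a range, not as the error rate of the plan. Baseline, cycle 1 and KIR data are little affected by sample loss, although a crude yes/no comparison would still be exposed if the marker predicts transplant. The primary RFS conclusion, the futility rule and the toxicity rule are not affected.

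**What to change.** Add a short paragraph to section 8.0:

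- Relate baseline values, and the change from baseline to day 28 of cycle 1, to RFS counted from a day-28 landmark in patients relapse-free at that point, with Kaplan-Meier curves and Cox regression. Day 28 precedes the first dose escalation that section 4.1.1 allows.
- Use later markers and MRD only with landmarks at the end of cycle 3 or 6, or as time-dependent covariates. Because section 4.1.1 lets residual disease prompt escalation, read MRD results alongside dose.
- Use only samples taken before relapse.
- Handle transplant as in the RFS analyses: censored, with a competing-risk analysis.
- Report the number at risk and the number sampled at each visit.
- Keep scatterplots as description, and state the visit each one shows.

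The cost is analysis code; no samples, visits or patients are added. The small downside is that a landmark analysis drops patients with an event before the landmark: about 6–8% at day 28 and 17–21% at the end of cycle 3, from the shares above.

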## **9.0 MEASUREMENT OF EFFECT**

### **9.1 Criteria for Response**

#### **9.1.1 Definitions**

Evaluable for toxicity. All patients will be evaluable for toxicity from the time of their first treatment on study.

Evaluable for response. Patients who have received at least one cycle of therapy, and have had their disease re-evaluated will be considered evaluable for response. These patients will have their response classified according to the definitions stated below. (Note: Patients who exhibit objective disease progression prior to the end of cycle 1 will also be considered evaluable.)

#### **9.1.2 Response Criteria**

Response Criteria are based on the Revised Recommendations of the International Working Group Response Criteria in Acute Myeloid Leukemia. They are summarized below.

#### **9.1.3 Complete remission (CR)**

Disappearance of all clinical and/or radiologic evidence of disease, including extramedullary leukemia. Neutrophil count  $\geq 1.0 \times 10^9/L$  and platelet count  $\geq 100 \times 10^9/L$ , and bone marrow differential showing  $\leq 5\%$  blasts.

#### **9.1.4 Complete remission without platelet recovery (CRi)**

Have met all criteria for CR, except for either residual neutropenia (ANC  $< 1.0 \times 10^9/L$ ) or thrombocytopenia (platelet count  $< 100 \times 10^9/L$ ).

#### **9.1.5 Partial remission (PR)**

Blood count recovery as for CR, but with a decrease in marrow blasts of at least 50% and not more than 6 to 25% abnormal cells in the bone marrow.

### **9.1.6 Confirmed Relapse**

Recurrence of disease as noted by: > 30% peripheral blasts, or > 20% bone marrow blasts. If the bone marrow blasts are between 6% and 20%, 2 serial bone marrow examinations at least 2 weeks apart demonstrating successive increase in blasts by at least 2% will also be a confirmed relapse.

### **9.1.7 Relapse-free survival (RFS)**

Time from CR or CRi until confirmed relapse or death.

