## 3.0 PATIENT SELECTION

### 3.1 Inclusion Criteria:

1. Patients aged 18 to 55 years with high risk (as defined in #2) AML who have achieved their **FIRST** CR or CRi within 12 months of enrollment and are not immediately candidates for allogeneic stem cell transplant. Patients above age 55 who are not eligible for other protocols may be considered for enrollment on a case by case basis after discussion with the PI.
2. Patients in their **FIRST** CR or CRi may be eligible for enrollment only if they have a high risk feature, including, but not limited to: adverse karyotype, FLT3 mutation, history of antecedent hematologic disorder (AHD), presence of dysplasia in the bone marrow, therapy-related AML, history of requiring more than 1 cycle of intensive induction chemotherapy to achieve first remission, or presence of persistent minimal residual disease (detected by cytogenetics, molecular markers, or flow cytometry) at any point after initial induction cycle. Patients aged > or = 18 years with AML who have achieved a **SECOND** CR or CRi within 12 months of enrollment and are not immediately candidates for allogeneic stem cell transplant are also eligible.
3. Patients should have received induction chemotherapy for AML and at least 1 consolidation.
4. Patients with history of extramedullary AML, except for CNS involvement that is currently controlled, will not be eligible for enrollment.
5. ECOG performance status of < or = 3
6. Adequate organ function as follows:
  - a. Serum total bilirubin < or = to 1.5 X the Upper Limit of Normal (ULN)
  - b. Serum creatinine < or = to 2.5 x ULN
7. Adequate BM reserve:
  - a. Absolute neutrophil count (ANC) > 0.5 x 10^9/L
  - b. Platelet count > or = 30 x 10^9/L

8. For females of childbearing age, they may participate if they:
  - a. Have a negative serum or urine pregnancy test within 10 to 14 days of enrolling  
(A second pregnancy test will be performed within 24hrs of starting therapy and both negative pregnancy tests will be required for starting therapy.)
  - b. Agree to either abstinence or 2 effective contraceptive methods throughout the treatment period and up to 28 days after discontinuing treatment.
9. For male patients with a female partner of childbearing age, they may participate if they agree to either abstinence or 2 effective contraceptive methods throughout the treatment period and up to 28 days after discontinuing treatment.

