Scenario	True Median (months)	Pr(Stopped Early)	Mean No. patients	Average Trial Duration (months)
1	4	0.968	18.9	21.5
2	6	0.410	37.7	30.6
3	8	0.102	46.4	34.8
4	10.5	0.030	48.9	36.0

5	12	0.017	49.3	36.2
---	----	-------	------	------

For the primary analysis of the efficacy endpoint, we will compute the Bayesian posterior probability of  $\text{Pr}(\lambda_E > \lambda_H + \delta | \text{data})$ . As a secondary analysis, we will perform a competing risk analysis treating stem cell transplant as a competing event for RFS.

In addition, we will continuously monitor treatment-related toxicities using the Bayesian approach of Thall, Simon, Estey (1995). Specifically, the trial will be stopped if  $\text{Prob}(\pi T > 0.30 | \text{data}) > 0.92$ , where  $\pi T$  is the toxicity rate and we assume a beta (0.6, 1.4) prior for  $\pi T$ . That is, if at any given time, there is more than 92% probability that the toxicity rate of the maintenance therapy with lenalidomide is greater than 30%, the trial will be stopped. For the purpose of toxicity monitoring, toxicities are defined as any treatment-related clinically significant grade 3 or 4 non-hematologic AEs occurred any time during the trial, which are also outlined in Table 2. We will apply this stopping rule starting from the 10th patient and in cohort size of 10. The stopping boundaries corresponding to this toxicity monitoring rule are described in the following table:

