### **9.1.8 Event-free survival (EFS)**

Time from treatment start until date of first documented event. Event will be defined as: confirmed relapse, withdrawal from study due to adverse event, or death due to any cause.

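### The primary endpoint, RFS, starts at treatment start in Section 8 but at CR or CRi in Section 9.1.7, with no statement of which prevails; 9.1.7 counts event-free time before the first dose and should be aligned

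*Combined protocol and SAP*

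**What the plan says.** Section 8 (Statistical Considerations) introduces RFS as the primary endpoint, "which is defined as the time interval from date of treatment start until the date of death or disease relapse". It then uses RFS twice. During accrual, "The study will be continuously monitored for the primary endpoint, RFS". At the end, "For the primary analysis of the efficacy endpoint, we will compute the Bayesian posterior probability of" the experimental median exceeding the historical median by more than 2.5 months. The benchmark is in the same place: "Our goal is to improve the median RFS from 8 months (based on historical treatment) to 10.5 months". Section 2.4 gives 8.5 months for untransplanted high-risk patients. Neither section says from what date the historical time was counted.

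Section 9.1.7 defines RFS differently: "Time from CR or CRi until confirmed relapse or death". In the same list, EFS (9.1.8) is "Time from treatment start until date of first documented event", and OS (9.1.10) also begins at treatment start. Only RFS and CR duration (9.1.9) begin at remission.

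On entry, Section 3.1 admits patients who have reached a first or second "CR or CRi within 12 months of enrollment and are not immediately candidates for allogeneic stem cell transplant". Its item 3 adds: "Patients should have received induction chemotherapy for AML and at least 1 consolidation". No section describes delayed entry or left truncation.

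The event wording differs too. Section 8 speaks of disease relapse, while 9.1.7 requires confirmed relapse, which 9.1.6 defines.

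**The concern.** In a trial that enrolled at the moment of remission the two clocks would nearly coincide. Here they cannot. Patients arrive after consolidation and up to a year after remission, and anyone who has relapsed or died in the meantime is not enrolled. The interval from remission to first dose is therefore event-free by eligibility. Counting it as time at risk lengthens RFS whether or not the drug works.

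RFS drives both the futility rule and the primary posterior probability. If the 9.1.7 clock were programmed without delayed entry, a poor drug would be stopped less often and an inactive drug would look better than it is.

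**Working it through.** **1. The clocks side by side.**

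| Measure | Section | Starts at |
|---|---|---|
| RFS | 8 | treatment start |
| RFS | 9.1.7 | CR or CRi |
| EFS | 9.1.8 | treatment start |
| CR duration | 9.1.9 | CR or CRi |
| OS | 9.1.10 | treatment start |

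Take a patient enrolled and first dosed 12 months after CR who dies in remission 3 months later. OS is 3 months. RFS is 3 months under Section 8 and 12 + 3 = 15 months under 9.1.7. RFS longer than OS is incoherent.

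**2. The model.** All inputs are from Section 8. RFS is exponential. The historical median follows IG(3.6, 20.8): mean 20.8/2.6 = 8, variance 64/1.6 = 40. The experimental median follows IG(2.128, 9.024): mean 9.024/1.128 = 8, variance 64/0.128 = 500. With D events and total time T, the experimental posterior is IG(2.128 + D, 9.024 + ln2 × T). The trial stops if Pr(experimental > historical + 2.5) < 0.05, looking from the 10th patient, with at most 50 patients and 12 months' further follow-up.

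**3. The plan's own table.** Time from entry, 2 patients per month as in the plan's simulation, no transplant, 8,000 trials per scenario:

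| True median (months) | 4 | 6 | 8 | 10.5 | 12 |
|---|---|---|---|---|---|
| Plan, stopped early | 0.968 | 0.410 | 0.102 | 0.030 | 0.017 |
| First look at 10 patients | 0.971 | 0.416 | 0.122 | 0.037 | 0.023 |
| First look at 11 patients | 0.971 | 0.410 | 0.122 | 0.030 | 0.017 |

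The match is close, except that the 8-month row is 0.02 high.

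**4. What a lag does, by hand.** The fitted median is ln2 × T/D. Adding a mean lag L to all 50 patients adds ln2 × 50 × L/D. At true median 8, the runs in step 5 average 35.7 events, so each month of lag adds 0.693 × 50/35.7 = 0.97 month. From 8.1 this predicts 9.1, 10.0 and 11.0 at lags of 1, 2 and 3 months.

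**5. Simulation with the lag.** The documents give only the 12-month limit, so mean lags of 1, 2 and 3 months are assumed. The historical 8 months is taken as counted from treatment start. Accrual is 1 patient per month (Section 8's expected rate), 25% are censored at transplant, and each cell has 3,000 trials. Final figures use all 50 patients and ignore early stopping.

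| Mean lag (months) | 0 | 1 | 2 | 3 |
|---|---|---|---|---|
| True median 4: stopped early | 0.95 | 0.68 | 0.25 | 0.04 |
| True median 4: mean enrolled | 18 | 31 | 43 | 49 |
| True median 4: mean final posterior | 0.02 | 0.06 | 0.14 | 0.24 |
| True median 6: stopped early | 0.43 | 0.12 | 0.02 | 0.00 |
| True median 6: mean final posterior | 0.16 | 0.26 | 0.37 | 0.47 |
| True median 8: fitted median | 8.1 | 9.0 | 10.0 | 11.0 |
| True median 8: mean final posterior | 0.38 | 0.48 | 0.57 | 0.64 |

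Repeat runs put the first row, at lags 1 to 3, at 0.68 to 0.70, 0.25 to 0.28 and 0.04 to 0.05; I quote about 0.70, 0.25 and 0.05. For comparison, a drug that truly meets the 10.5-month target, timed from treatment start, averages a final posterior of about 0.62.

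**6. Sensitivity.** The shape of the lag hardly matters. At mean lag 2 and true median 4, early stopping is 0.245 with lags uniform on 0 to 4 months, 0.240 on 1 to 3, and 0.235 with a fixed lag. At 2 patients per month with fixed lags and no transplant, the true-median-4 row is 0.97, 0.77, 0.31 and 0.04.

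**The case against.** The strongest reply is that nobody would use 9.1.7. Section 8 contains the explicit definition of the primary endpoint together with everything that acts on it, whereas 9.1.7 sits in a list of response criteria that specifies no analysis. A statistician who follows Section 8 incurs none of the lag effects shown. The figures size a misreading, with lags that no section gives.

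Most of this stands. It makes the harm conditional and the point a consistency correction rather than a fault in the design. It does not remove the point. No sentence gives precedence, and Section 9 is where the other time-to-event endpoints are defined, so someone programming from it would take the wrong clock for RFS.

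A reader might also infer several stronger things that the documents do not support:

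- *That the published operating characteristics are wrong.* They assume no pre-dose offset and are consistent with Section 8.
- *That the match in step 3 proves which clock was meant.* A simulator drawing times from entry would print such a table under either definition. The case for Section 8 rests on the structure of the document.
- *That late stopping is the main harm, because a poor drug still ends with a low posterior.* This fits true medians of 4 and 6 months. It fails for an inactive drug, which at lag 3 reaches 0.64.
- *That the false-positive rate is inflated by a known amount.* No success threshold is stated, so no such rate is defined.

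**Conclusion.** The contradiction is real and in current text, and 9.1.7 as written does not suit this trial. It should be fixed because it concerns the primary endpoint.

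If 9.1.7 were used without delayed entry, and under the assumptions in step 5, there are two harms, and neither is shown to be the larger. Futility protection weakens sharply. And an inactive drug looks better: at a mean lag of 3 months its mean posterior is about that of a correctly timed drug at the 10.5-month target.

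It would go too far to say that following Section 8 settles the matter. Its clock removes the pre-dose event-free time. The comparison with history can be relied on only if the historical patients were timed from a matching origin and selected in the same way, and the documents state neither. Under a strictly constant hazard, a historical 8 months counted from CR in unselected patients would still be 8.0 from treatment start, but that follows from the exponential model and is not a documented fact about those patients.

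**What to change.** Replace 9.1.7 with: *RFS is the time from the date of treatment start to confirmed relapse (Section 9.1.6) or death from any cause, whichever comes first.* Put the same sentence in Section 8, which also settles the event wording, and state that it governs futility monitoring and the primary analysis. State the time origin of the historical 8 (8.5) months, and whether those patients were selected as still in remission at that origin.

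Optional note: CR duration may keep its start at remission, but would then be better analysed with left truncation at treatment start.

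The cost is a few sentences, with no new patients, visits or procedures. There are two downsides. Reported RFS will be shorter than under 9.1.7. And if the historical figure proves to have been counted from CR, the IG(3.6, 20.8) prior and the operating-characteristics table may need to be redone.
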